1.0 SYNOPSIS

[figure not shown]
Title:	MediGuide Registry
Acronym:	None
Purpose:	The goal of this registry/observational study is to collect data on the clinical utility of MediGuide™ system in CRT implantation and EP procedures
Objectives:	
The intent of this worldwide registry/observational study is to understand the utility of the MediGuide™ technology in real world clinical practice during CRT implantation and study-specific-EP procedures. The study should provide an understanding of the effect of MediGuide™ technology on:
 
 • The amount of fluoroscopy time and the radiation exposure • Total procedure time • Peri-procedural clinical event rate 
Additionally, this study will address the following
 
 • Identification of procedural challenges which may aid in developing future MediGuide tools • Evaluation of newly available MediGuide tools during the study • Correlation between MediGuide operator experience and the radiation exposure amount and time
Design:	This is a worldwide, multicenter, non-randomized registry/observational study. The study will enroll up to 1000 patients from up to 65 centers undergoing either CRT implantation or an EP procedure. The study will enroll a minimum of 250 patients for each group. Patients who are undergoing either procedure at study centers equipped with MediGuide™ technology utilizing market approved MediGuide™-enabled tools will be eligible to participate in this study. This study may continue for up to 3 years, depending on the rate of enrollment.
Devices Used:	Market-approved MediGuide™-enabled tools and software
Study Population	
CRT Group All patients from participating sites who are indicated for a CRT-D/P device implant, including an upgrade with a new LV lead implant and are implanted with St. Jude Medical pulse generators and willing to provide

	
written Informed Consent can be enrolled in this study. Patients can be implanted with non-St. Jude Medical leads
 
EP Group All patients from participating sites who are indicated for an atrial fibrillation, atrial flutter or VT ablation procedure for which market approved MediGuide™-enabled ablation catheter is available and willing to provide written Informed Consent can be enrolled in this study.

Data Collection	
Data collection schedule
 
 • CRT patients: Data will be collected for patients undergoing CRT implantation at implant and pre-discharge . • EP procedures: Data will be collected for patients undergoing an EP procedure at the time of the procedure and pre-discharge.

2.0 BACKGROUND AND JUSTIFICATION FOR CLINICAL STUDY

The number of fluoroscopically-guided minimally invasive diagnostic and therapeutic procedures has greatly increased in recent years.¹ However, the potential injuries from the associated radiation exposure are often underestimated. The radiation dose for some interventional procedures may be several orders of magnitude greater than that for simple radiographic studies.^{2, 3} Once the dose exceeds a certain limit, the injury becomes progressively more severe with increasing dose, although the true severity of major injuries will only become apparent weeks to months after the procedure.⁴ Very high doses usually produce some symptoms within 24 hours of the procedure. Furthermore, it is known that even sub-threshold exposure to radiation under recommended occupational limits has been shown to increase the chance of life-time cancer.⁵ The core principle governing the use of ionizing radiation is ALARA (as low as reasonably achievable) and according to this principle there is no magnitude of radiation exposure that is known to be completely safe.^{6, 7} This principle confers a responsibility on all physicians to minimize the radiation injury hazard to their patients, to their staff, and to themselves.

St. Jude Medical ((hereinafter referred to as SJM) has developed a novel 3D electromagnetic navigation system (MediGuide™) that is capable of non-fluoroscopic navigation of sensor-enabled tools in the x-ray environment. By projecting the tool's position and orientation onto the pre-recorded fluoroscopic images, the system allows for tracking of tools within pre-recorded x-ray loops while compensating for primary and secondary organ motion, thus reducing x-ray exposure during diagnostic and therapeutic cardiac procedures for which MediGuide™-enabled tools are available.

Previous single-center studies have shown that the application of the MediGuide™ technology can lead to a significant reduction in fluoroscopy burden during ablations of atrial flutter, SVT, and atrial fibrillation.⁸⁻¹² In a recent single-center registry,¹³ the MediGuide™ navigation system was used for over 600 cases of ablations for atrial flutter, atrial fibrillation and ventricular tachycardia and implantation of cardiac resynchronization therapy (CRT) devices. In these cases, the median fluoroscopy time was not only reduced compared to the traditional fluoroscopy time but the complication rate was lower than previously-published data. It was also observed by the same group that the total fluoroscopy time and the exposure to radiation was reduced further as the operator gained more experience in working with MediGuide™ system and tools.¹⁴ However, these studies were all conducted at a single center and the radiation reduction benefit, complication rate, and operator proficiency across clinics at different geographies are unknown.

The MediGuide registry is sponsored by SJM. The goal of this study is to collect data on the clinical utility of MediGuide™ system in CRT implantation and study-specific EP procedures.

3.0 RISKS AND BENEFITS OF THE CLINICAL STUDY

The risks involved with this study are similar to those associated with MediGuide™ enabled implantation of commercially available CRT systems and MediGuide™ enabled ablation procedures with commercially available ablation tools. There are no additional risks to the patients enrolled in this study.

3.1 Description of subject population

Approximately 1000 patients undergoing CRT implant or study-specific EP procedures at study centers equipped with MediGuide™ technology utilizing market approved MediGuide™-enabled tools will participate in this study.

3.2 Anticipated clinical benefits

Patients participating in this study may be exposed to less radiation due to the reduced fluoroscopy use when using the MediGuide™ system.

3.3 Potential reportable adverse events

Anticipated adverse events
Adult respiratory distress syndrome (ARSD)
Air embolism
Allergic reactions to contrast media (agents)
Anemia
Anesthesia reaction
Arrest (cardio)
Arrest (respiratory)
Arrhythmias
AV fistula
Bleeding (non-hematoma)
Cardiac Perforation
Cardiac Tamponade
Cardiac thromboembolism
Cerebrovascular accident/attack
Chest pain/discomfort
Complete AV block
Component damage to ICD or PM
Coronary artery spasm
Coronary artery thrombosis
Coronary sinus dissection

Coronary sinus perforation
Death
Decompensated Heart Failure
Diaphragmatic paralysis
Elevated pacing thresholds
Endocarditis
Erosion/extrusion
Exacerbation of pre-existing atrial fibrillation
Gastroparesis
Hematoma
Hemothorax
High DFTs
Infection
Lead dislodgement or lead migration
Lead fracture
Lead insulation damage
Loss of capture
Loss of sensing
Left atrial esophageal fistula
Myocardial Infarction
New or worsened angina
Oversensing
Oversensing resulting in therapy
Pacemaker mediated tachycardia (PMT)
Pectoral stimulation
Pericardial effusion
Pericarditis
Phrenic nerve injury
Phrenic nerve/diaphragmatic stimulation
Pneumothorax
Premature battery depletion

Prolonged detection of redetection time
Pulse generator malfunction
Pseudoaneurysm
Pulmonary edema
Pulmonary embolism
Pulmonary vein stenosis
Shock/Hypotension
Stroke
Syncope unknown etiology
Therapy for non-ventricular rhythm
Thromboembolism
Thrombosis
Transient ischemic attack (TIA)
Undersensing
Valvular damage
Vascular access complications
Vasovagal reactions
Ventricular arrhythmia

4.0 STUDY DESIGN

4.1 Purpose

The intent of this worldwide registry/observational study is to understand the utility of the MediGuide™ technology in real world clinical practice during CRT implantation and study-specific-EP procedures. The study should provide an understanding of the effect of MediGuide™ technology on:

- The amount of fluoroscopy time and the radiation exposure
- Total procedure time
- Peri-procedural clinical event rate

Additionally, this study will address the following

- Identification of procedural challenges which future MediGuide tools can potentially address
- Evaluation of newly available tools during the study

- Correlation between MediGuide™ operator experience and the radiation exposure amount and time

This study may continue for up to 3 years, depending on the rate of enrollment and follow-up timelines.

4.2 Study Design and Scope

This is a worldwide, multicenter, non-randomized registry/observational study. The study will enroll up to 1000 patients from up to 65 centers undergoing either CRT implantation or an EP procedure. The study will enroll a minimum of 250 patients for each group. Patients who are undergoing either procedure at study sites equipped with MediGuide™ technology utilizing market approved MediGuide™-enabled tools will be eligible to participate in this study.

Data collection schedule

- CRT Group: Data will be collected for patients undergoing CRT implantation at implant and pre-discharge.
- EP Group: Data will be collected for patients undergoing an EP procedure at the time of the procedure and pre-discharge.

4.3 Inclusion and Exclusion Criteria

CRT Group

All patients from participating sites who are indicated for a CRT-D/P device implant, including an upgrade with a new LV lead implant and are implanted with St. Jude Medical pulse generators and willing to provide written Informed Consent can be enrolled in this study. Patients can be implanted with non-St. Jude Medical leads.

EP Group

All patients from participating sites who are indicated for an atrial fibrillation, atrial flutter or VT ablation procedure for which market approved MediGuide™-enabled ablation catheter is available and willing to provide written Informed Consent can be enrolled in this study.

4.4 Subject Population

4.4.1 Subject Screening

All subjects presenting at the study site can be screened by a member of the study team previously trained on the CIP and delegated to do so.

Subjects who do not meet the inclusion/exclusion criteria will not be eligible to participate in this study.

Subjects meeting the inclusion/exclusion criteria will be fully informed about the study and asked to participate in the study. In case the subject agrees, a duly signed and dated Patient Informed Consent will be obtained.

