4.4.2 Point of Enrollment

Subjects are considered enrolled in the study if the subject has provided written Patient Informed Consent and CRT implant or an EP procedure was attempted.

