6.6 Subject study completion

Patient participation in the study is complete upon completion of pre-discharge visit. When the subject's participation in the clinical study has been completed the subject will return to the medical care as per physician's recommendation.

6.7 Any Known or Foreseeable Factors that May Compromise the Outcome of the Clinical Study or the Interpretation of the Results

All foreseeable factors that may compromise the outcome have been taken into account by clinical study design and well defined subject selection criteria.

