12.2 Sample size

This is a worldwide, multicenter, non-randomized registry/observational study that aims to enroll up to 1000 patients from up to 65 centers undergoing either CRT implantation or an EP procedure. The study will enroll a minimum of 250 patients for each group. This sample size was chosen to provide understanding on the effect of following MediGuide™ technology on.

- The amount of fluoroscopy time and the radiation exposure
- Total procedure time
- Peri-procedural clinical event rate

12.3 In multi-center studies, the minimum and maximum number of subjects to be included for each center

The maximum number of subjects that each center can enroll is 50 patients.

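### Whom to screen is left to each site and no record of eligible patients not enrolled is described, so selection could move the real-world estimates in either direction and could be neither confirmed nor excluded

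*Combined protocol and SAP*

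**What the plan says.** The target of the registry, in section 4.1, is the usefulness of the technology "in real world clinical practice". Four places govern who enters.

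- Section 4.4.1: "All subjects presenting at the study site can be screened", by a trained and delegated member of the study team. It then adds a mandatory step: "Subjects meeting the inclusion/exclusion criteria will be fully informed about the study and asked to participate in the study".
- Section 4.3, for both groups: patients who are eligible and "willing to provide written Informed Consent can be enrolled in this study".
- Section 4.4.2: a patient counts as enrolled who "has provided written Patient Informed Consent and CRT implant or an EP procedure was attempted".
- Section 12.3: "The maximum number of subjects that each center can enroll is 50 patients". Section 12.2 sets an overall ceiling of 1000 patients and 65 centres, with at least 250 patients per group.

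Section 12.1 plans descriptive summaries with 95% confidence intervals and no case-mix adjustment. Section 10.0 describes central review of submitted data. Section 6.7 states: "All foreseeable factors that may compromise the outcome have been taken into account".

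**The concern.** The registry exists because, as section 2.0 says, results so far come from single centres, and radiation benefit, complication rate and operator proficiency elsewhere are unknown. That purpose needs enrolled patients who resemble those treated. A site can follow the plan to the letter and still screen only some of the patients it treats. Passing over an unscreened patient breaks no rule, so it is not a deviation and leaves no study record.

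Two features raise the stakes. There is no concurrent control, so readers will naturally set the results beside outside figures, as the background already does, and that comparison is sensitive to case mix. The plan also relates operator experience to radiation exposure; if the cases chosen change as experience grows, selection is mixed with learning. Section 6.7 relies on well-defined criteria, but criteria settle who may enter, not who is approached.

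**Working it through.** **The text.** The permissive screening sentence comes first and the mandatory invitation second. The invitation protects only patients already found to meet the criteria, so the open step is the choice of whom to screen. None of the supplied sections asks for consecutive entry, a screening log, a count of eligible patients or reasons for non-enrolment.

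**Does the centre cap force sequential entry?** No. 65 × 50 = 3250 places for at most 1000 patients, an average of 1000/65 = 15.4 per centre; 1000/50 = 20 full centres would suffice. The cap limits one centre's weight, not its choice of cases.

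**The plan's own figures.** The 1000 and 250 come with no standard deviation, event rate or precision target, so there is no calculation to reproduce.

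**Illustration of size.** Every input here is an assumption. Let *s* be the share of hard cases among eligible patients and *r* their enrolment rate relative to the others. The enrolled share of hard cases is *s′* = *sr*/(*sr* + 1 − *s*). With fluoroscopy time 1 (easy) and 2.5 (hard), the mean is 1 + 1.5*s′*. With events 4% and 12%, the rate is 4% + 8% × *s′*.

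| *s* | *r* | *s′* | Mean fluoroscopy | Change | Event rate | Change |
|---|---|---|---|---|---|---|
| 0.20 | 1 | 0.200 | 1.300 | none | 5.60% | none |
| 0.20 | 0.5 | 0.111 | 1.167 | −10.3% | 4.89% | −12.7% |
| 0.20 | 1.5 | 0.273 | 1.409 | +8.4% | 6.18% | +10.4% |
| 0.30 | 1 | 0.300 | 1.450 | none | 6.40% | none |
| 0.30 | 0.5 | 0.176 | 1.265 | −12.8% | 5.41% | −15.4% |
| 0.30 | 1.5 | 0.391 | 1.587 | +9.4% | 7.13% | +11.4% |

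**Against sampling error.**

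- Mean, coefficient of variation 1 (assumed): 1.96/√250 = 0.124, or 12.4%. At 750, the most one group can reach if the other has 250 (1000 − 250), it is 1.96/√750 = 0.072, or 7.2%.
- Events at *n* = 250: 1.96 × √(0.056 × 0.944/250) = 2.9 percentage points, and 1.96 × √(0.064 × 0.936/250) = 3.0. The half-rate shifts are 5.60 − 4.89 = 0.71 and 6.40 − 5.41 = 0.99 points, well inside those widths.

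**Coverage.** If hard cases have means *D* standard deviations higher, bias in standard-error units is *b* = *D*(*s′* − *s*)√*n*, and coverage of the nominal 95% interval is Φ(1.96 − *b*) − Φ(−1.96 − *b*). With *s* = 0.30, *r* = 0.5 and *D* = 0.5 to 1.0, the bias is −0.06 to −0.12 SD. Coverage is 84% to 50% at *n* = 250 and 61% to 8% at *n* = 750. More patients do not help, because the interval narrows around a displaced value.

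**The case against.** The strongest reply is that this is a descriptive registry with no hypothesis test, and section 4.4.1 already requires patients who meet the criteria to be invited. That sentence stands, and it narrows the gap to the choice of whom to screen. It does not close it, because without a record of eligible patients compliance cannot be checked.

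A reader might infer several stronger things that the documents do not support.

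- That operators pick their own cases. Screening may be done by any trained, delegated team member, and section 4.5.1 gives consent to the principal investigator or a designee. Roles may overlap, but the text does not say so. Consent before study procedures and counting of attempted procedures also limit selection on the observed result.
- That the results will be biased low. Favouring complex cases would bias them upward; the direction cannot be derived.
- That planned enrolment is sparse beside the single-centre experience of over 600 cases in section 2.0. The patient, centre and duration figures are all ceilings and the 600 has no stated period, so no annual rate can be compared. Low counts could also reflect few eligible patients.
- That selection would be invisible. Section 6.3 records history, ejection fraction, NYHA class (CRT patients), venous anatomy, ablation site and personnel experience, so enrolled case mix can be described and compared between centres. That is useful but does not replace a denominator.

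A log may also exist in the case report forms, the data management plan or pages not supplied. The fair statement is that none is described.

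**Conclusion.** The gap is real and worth closing as a cheap improvement. The plan lets sites choose whom to screen and describes no way to learn what share of eligible patients entered. Selective enrolment could therefore bias the main estimates in either direction and could be neither confirmed nor excluded.

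The size is not known. Under the assumed half-rate enrolment of hard cases, the shift in mean fluoroscopy time (10–13%) is about as large as the sampling half-width at the group minimum (12.4%) and larger than it at 750 (7.2%). The event-rate shift (13–15% relative, 0.7 to 1.0 percentage points) is smaller than its sampling error at 250. These figures rest wholly on the assumed share, difficulty and enrolment ratio. They show what is possible and are not an estimate of bias in this study.

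**What to change.** - **4.4.1:** require that consecutive patients scheduled for an eligible MediGuide procedure are screened and, if they meet the criteria, invited, for as long as enrolment for that group is open at the centre. Make this subject to the 50-per-centre cap, the 1000 total and the 250-per-group minimum, so that one procedure type cannot fill the study.
- **Log:** one anonymised line per eligible case, giving date, procedure type, enrolled or not, and reason. If consecutive invitation proves impractical somewhere, the log alone still makes selection visible. It shows selection into the registry, not the prior decision to use MediGuide.
- **12.1:** report enrolled over eligible by centre and group beside the main results, with a sensitivity analysis by capture fraction using a cut-off fixed before analysis.
- **6.7:** name selective enrolment as a foreseeable factor and point to the log.
- **Related wording:** the CRT criterion in 4.3 ("and are implanted with St. Jude Medical pulse generators") and enrolment at an attempted procedure in 4.4.2 should be reconciled, so that it is clear whether failed implants are counted.

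The cost is a protocol wording change and a modest log burden, heavier at high-volume centres. No visits, procedures or patients are added. Eligible cases missed before the change cannot be reliably reconstructed, so it is best made early.

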4.4.2 Point of Enrollment

Subjects are considered enrolled in the study if the subject has provided written Patient Informed Consent and CRT implant or an EP procedure was attempted.

4.4.3 Description of the IRB/EC specific responsibilities

IRB/EC approval for the study and informed consent will be required prior to beginning the study. A copy of the IRB/EC approval and corresponding informed consent must be forwarded to SJM prior to authorization of the institution to begin the study. Any withdrawal of IRB /EC approval should be reported to SJM within 5 working days of the withdrawal of approval. A list of IRBs/ECs for Institutions participating in the study will be provided upon request.

4.5 Informed Consent Process

4.5.1 General process

Prior to enrolling in the clinical study and conducting study-specific procedures, all subjects will be consented, as required by applicable regulations and the center's IRB/EC. Informed consent must be obtained from each subject prior to any study related procedures. The consent form must be signed and dated by the subject and by the person obtaining the consent.

The principal investigator or his/her authorized designee will conduct the Informed Consent Process. This process will include a verbal discussion with the subject on all aspects of the clinical study that are relevant to the subject's decision to participate in the clinical study.

The subject shall be provided with the informed consent form that is written in a language that is understandable to the subject and has been approved by the center's IRB/EC. Failure to obtain informed consent from a subject prior to study enrollment should be reported to SJM within 5 working days and to the reviewing center's IRB/EC consistent with the center's IRB/EC reporting requirements.

5.0 DEVICE UNDER INVESTIGATION AND CONTROL/COMPARATORS (IF APPLICABLE)

[figure not shown]
5.1 Device Description

In this study, any market approved MediGuide™-enabled tools and software will be used.

6.0 PROCEDURES

6.1 Study Flow Chart

Figure 2: Flow Chart

6.2 Procedures

The clinical study will be conducted in accordance with the CIP. All parties participating in the conduct of the clinical study will be qualified by education, training, or experience to perform their tasks, and this training will be documented appropriately.

The clinical study will not commence until SJM receives written approval from the IRB/EC and relevant regulatory authorities and all required documents have been collected from the site(s).

Upon site activation, participating clinician’s previous experience in performing CRT or EP cases with or without utilizing MediGuide™ enabled tools will be collected via one-time survey.

Table 1: List of all study specific activities/procedures

	CRT Group at Enrollment	EP Group at Enrollment	Discharge
Baseline Demography	X	X	
Medical History	X	X	
Medications	X	X	
12 Lead ECG (most recent)	X		
Echo Measurements (including most recent LVEF)	X	X	
NYHA	X		
Device Session Record	X		
Fluoro Time and Radiation Dose	X	X	
Electrical Lead Measurements for the RA, RV and LV Leads	X		
Reportable Adverse Event/Health Care Utilization	(X)	(X)	(X)
Fluoroscopic Views and Orientation Angles Used	X	X	

(X) if applicable

